7.2 Statistical Methods

Descriptive statistics will be used for all primary and secondary endpoints, when appropriate.

We will define outcome measures on the basis of the change for each subject from baseline to each follow-up point, controlling for chance imbalances in the mean baseline values between treatment groups. A Wilcoxon Signed-rank test will be used for paired comparison of quantitative variables (OSDI score) between the baseline and each post-baseline time points. Chi-square test will be used to compare qualitative variables (Investigator's rating scale/ changes in concomitant medications) between the 2 groups. Two-sided $P < .05$ will be considered statistically significant for all comparisons. 95% Confidence interval will be provided for comparison between the investigational drug and placebo for the primary efficacy, the primary safety, and the secondary endpoints.

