Net	Neutrophil extracellular trap
OSDI	Ocular Surface Disease Index
Otc	Over the counter
QID	Four times per day
rhDNase1	Recombinant human deoxyribonuclease I
SAE	Serious Adverse Event
SGL	Subject Global Assessment
SP	Substance P
UIC	University of Illinois at Chicago
VA	Visual Acuity
VAS	Visual Analog Scale

Study Summary

Title	A Phase I/II Randomized Placebo-Controlled, Double-Blind Single-Center, tolerability and preliminary efficacy clinical trial of recombinant human deoxyribonuclease (rhDNase) eye drops in patients with dry eye disease.
Short Title	DNase treatment for dry eyes
Protocol Number	UIC-CNBL-1001
Phase	Phase I/II
Methodology	Double-blind
Study Duration	10 weeks
Study Center(s)	Single-center
Objectives	To evaluate the tolerability and preliminary efficacy of rhDNase1 eye drops in patients with Dry Eye Disease.
Number of Subjects	72 (study drug at least 30, placebo at least 30)
Diagnosis and Main Inclusion Criteria	Men and women ≥ 18 years of age with a diagnosis of established Dry Eye Disease, with Schirmer I < 10 , Ocular surface staining ≥ 1 and OSDI mild (≥ 13).
Study Product, Dose, Route, Regimen	Study drug: rhDNase1 (Pulmozyme®), 0.1% eye drops four times a day for eight weeks. Control: drug vehicle eye drops four times a day for eight weeks.
Duration of administration	8 weeks
Reference therapy	None
Statistical Methodology	Descriptive statistics will be used for all primary and safety endpoints, when appropriate. A Wilcoxon test will be used to compare changes in subjective symptoms from Baseline to follow-up values at 2 weeks, 4 weeks, 6 weeks, 8 weeks and 10 weeks. Primary efficacy measure is the change in the OSDI reported between Baseline and Week 8. Primary safety measure is the proportion of patients at week 8 who were able to successfully complete a full eight weeks of therapy with topical administration four times per day (q.i.d).

1 Introduction

This document is a protocol for a human research study. This study is to be conducted according to US and international standards of Good Clinical Practice (FDA Title 21 part 312 and International Conference on Harmonization guidelines), applicable government regulations and Institutional research policies and procedures.

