7.3 Subject Population(s) for Analysis

Subject population for analysis will include any subject enrolled in the study who received at least two weeks of treatment with study eye drops and attended at least the first post-treatment (week 2) follow up visit.

8 Safety and Adverse Events

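### The only test named for OSDI is a before-after signed-rank test, and the promised drug-placebo interval has no estimator, no baseline model and no stated role in deciding efficacy

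*Combined protocol and SAP*

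**What the plan says.** The Study Summary states: "Primary efficacy measure is the change in the OSDI reported between Baseline and Week 8". Section 3.2 likewise places the primary efficacy endpoints after 8 weeks of treatment, with OSDI first, followed by Rose Bengal staining and ocular redness.

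On method, section 7.2 makes five statements that bear on this point:

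- For OSDI: "A Wilcoxon Signed-rank test will be used for paired comparison of quantitative variables (OSDI score) between the baseline and each post-baseline time points".
- For qualitative variables, a chi-square test. This is the only test said to be between groups: "rating scale/ changes in concomitant medications) between the 2 groups".
- Outcomes are changes from baseline, "controlling for chance imbalances in the mean baseline values between treatment groups".
- A p-value below 0.05, two-sided, "will be considered statistically significant for all comparisons".
- On drug against placebo, the plan promises an interval: "95% Confidence interval will be provided for comparison between the investigational drug and placebo for the primary efficacy", and also for the primary safety and the secondary endpoints.

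The Study Summary describes the test less specifically: "A Wilcoxon test will be used to compare changes in subjective symptoms from Baseline to follow-up values" at weeks 2 to 10. It names no groups, and a Wilcoxon test may be signed-rank or rank-sum. Section 7.3 analyses subjects who "received at least two weeks of treatment with study eye drops and attended at least the first post-treatment (week 2) follow up visit".

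**The concern.** The trial has a vehicle arm so that change on drug can be separated from change that would have happened anyway. A signed-rank test of baseline against a later visit has no treatment term. Run in the drug arm, it asks whether OSDI moved, not whether it moved more than on vehicle. Run on both arms together, it does not involve treatment at all. Section 7.2 does not say which is meant.

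The promised interval is the right kind of quantity, but it is undefined. It could be a difference in mean or median change, or a baseline-adjusted difference. Since P < .05 applies to every comparison, the report could contain a significant fall in OSDI on drug and a drug-placebo interval that includes zero, and the plan has no rule for which one counts. An estimator left open can also be settled after the data are seen.

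**Working it through.** **1. What each stated method can do for the primary question.**

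| Method in 7.2 | Applied to | Compares drug with placebo? | Adjusts for baseline? |
|---|---|---|---|
| Signed-rank | OSDI, baseline v each visit | No | No |
| Chi-square | Qualitative variables | Yes | No |
| 95% CI | Primary efficacy and other endpoints | Yes | Not stated; no estimator |

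So no named test of OSDI compares the arms, and no named method carries out the promised baseline control. The same gap applies to staining and redness in section 3.2, for which 7.2 names no between-arm method beyond the undefined interval.

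**2. Inputs for the size.** 30 completers per arm is the intention in section 7.1. Two-sided 0.05 is from section 7.2. The documents give no SD for OSDI change and no expected change on vehicle. The shared change d, in SDs of change and equal in both arms, is therefore an assumption. There is no true drug effect. The plan states no power figure that could be reproduced.

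**3. Approximate rate by formula.** The chance that the drug arm shows a significant improvement is about P(Z > 1.96 − d√30), with √30 = 5.48:

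- d = −0.2: P(Z > 3.06) ≈ 0.1%
- d = 0: P(Z > 1.96) = 2.5%
- d = 0.1: P(Z > 1.41) ≈ 8%
- d = 0.2: P(Z > 0.86) ≈ 19%
- d = 0.3: P(Z > 0.32) ≈ 37%

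**4. Simulation with the signed-rank test itself.** 4,000 trials per setting; baseline and week 8 bivariate normal with correlation 0.5. A significant improvement means p < .05 with a positive median improvement.

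| Shared change d | Drug arm significantly improved | Drug significant, placebo not |
|---|---|---|
| −0.2 (worsening) | 0.1% | 0.1% |
| 0 | 2.3% | 2.2% |
| 0.1 | 7.5% | 6.8% |
| 0.2 | 18.4% | 15.2% |
| 0.3 | 34.4% | 23.8% |

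A second run gave 32% at d = 0.3, hence about 33%. The signed-rank rates lie a little below the normal formula, as expected. Between-arm tests on the same kind of data stayed near 5% whatever the shared change: rank-sum on change 4.3 to 5.2%, ANCOVA 4.5 to 5.4%.

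**5. Does the open estimator matter?** In units of the OSDI SD, with an assumed baseline to week 8 correlation r = 0.5, the 95% half-width is:

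- unadjusted change: 2.00 × √(2(1 − 0.5) × 2/30) = 2.00 × 0.258 = 0.52
- ANCOVA: 2.00 × √((1 − 0.25) × 2/30) = 2.00 × 0.224 = 0.45

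At r = 0.4 the pair is 0.57 and 0.47; at r = 0.7 it is 0.40 and 0.37. Different choices give visibly different intervals. If the promise to control baseline imbalance already excludes the unadjusted change, this cost falls away, so I give it little weight.

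**The case against.** The strongest reply is that a between-arm comparison is plainly intended. Section 7.2 promises a drug-placebo interval for primary efficacy and control of imbalance between the groups, and no sentence makes a within-arm p-value the criterion for efficacy. A 95% interval excluding zero could be taken as the counterpart of P < .05. This stands in part. A reader might infer that the plan compares the arms nowhere, or that it will declare efficacy on the signed-rank test; the documents support neither. What remains is that the decisive role of the interval is at best implied, while the one test spelled out for OSDI is the wrong one for that role.

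A reader of section 7.2 alone might also infer that the comparison has no fixed time point. That is not supported: the interval is for primary efficacy, which the Study Summary and section 3.2 fix at week 8.

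The error rates depend on a shared improvement that the documents do not predict. Section 1.5 warns of possible worsening when Restasis is held and on placebo, and under worsening the rate falls below 2%. One design feature could produce shared improvement: entry requires OSDI of at least 13, and OSDI is first scheduled on Day 1, which is also baseline. If that score is the qualifying one, regression to the mean gives d of roughly 0.01 to 0.32, depending on the assumed distribution and correlation. Rates for larger shared changes have no footing in the documents.

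Finally, this is a Phase I/II study of tolerability and preliminary efficacy, and 7.2 opens with descriptive statistics. That lowers the stakes, but section 2 names efficacy as a primary objective and 7.2 sets a significance threshold, so the plan should say what that threshold applies to.

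**Conclusion.** The concern holds. Section 7.2 names no between-arm test, estimator or baseline model for week 8 OSDI change, and does not say whether the drug-placebo interval or the signed-rank p-value decides efficacy. This is more than missing detail, because the one test given for OSDI answers a before-after question in a placebo-controlled trial.

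The size is conditional on the within-arm p-value being read as efficacy. In that case the chance of a false claim is about 2% with no shared change, and rises to 18% and about 33% at assumed shared improvements of 0.2 and 0.3 SD. If the interval is treated as decisive, that inflation does not occur, and what remains is an estimator that can be chosen late.

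**What to change.** In section 7.2 and the Study Summary, before unblinding:

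- State that the primary efficacy analysis is the between-arm difference in week 8 OSDI adjusted for baseline OSDI, and that its 95% CI and two-sided p-value decide efficacy.
- Choose the model now. ANCOVA is enough. A repeated-measures model over weeks 2 to 8 (treatment, visit, treatment-by-visit, baseline OSDI) would let subjects in the section 7.3 set without a week 8 value contribute, assuming missing at random; its covariance structure and degrees-of-freedom method should then be named. The gain is small: in simulation with a true effect of 0.50 SD and about 20% leaving after observed worsening, it averaged 0.49 to 0.50 against 0.48 for ANCOVA in completers, with the same spread.
- Add a rank-sum test on week 8 change as a sensitivity analysis, and label the signed-rank tests descriptive.
- Use a baseline-adjusted between-arm comparison for staining and redness too. For staining, which is measured only at screening and week 8, the baseline is the screening value. Both eyes are examined, so use one value per subject, such as the mean of the two eyes, or a model that accounts for paired eyes.

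The cost is rewording and slightly more analysis. No new data, visits or patients are needed.

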3.2 Primary Study Endpoints

Primary Efficacy End Point: The primary end points after 8 weeks of treatment include the following: (1) the change in the Ocular Surface Disease Index (OSDI) which is a patient subjective rating scale; the Clinical Global Impression (CGI) of change in dry eye disease symptoms (physician's rating) and Subject Global Assessment (SGA) of overall change from baseline (patient's rating) will serve as anchors to OSDI, as has been described previously²⁹; (2) a mean reduction in ocular surface staining as measured by Rose Bengal dye staining and (3) the change in ocular surface redness score OR slit-lamp examination.

Primary Tolerability End Point: The change in the test substance tolerance between Day 1 (post-dose) and at weeks 2, 4, 6 and 8.

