3.2.2 Efficacy End Point: Clinical Global Impression (CGI)

At each visit, the physician (Principal Investigator) will use his clinical evaluation (all signs and symptoms taken together) to provide a global assessment of the patients' change in Dry Eye symptoms and signs. The CGI is as follows:

Question (to physician): In general, compared with the patients' dry eye symptoms and signs at baseline, how would you characterize his/ her overall signs and symptoms now?

The responses will be categorized on a seven point scale as follows:

- Marked worsening
- Moderate worsening
- Minimal worsening
- Unchanged
- Minimal improvement
- Moderate improvement
- Marked improvement

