5.3 Method for Assigning Subjects to Treatment Groups

This Randomized placebo-controlled trial will have two study groups. Subjects will be randomly assigned to one of two groups (#1, #2). Group #1 will receive placebo (drug vehicle; control group) and Group #2 will receive study drug (rhDNase 0.1%; test group). We will use a computer-based random code generator (Research Randomizer; <http://randomizer.org/>) to generate 1 set of 72 non-unique, unsorted numbers with a range from 1 to 2 representing the group number (#1 is control group, #2 is test group). Each subject will be assigned a study identification (ID) number at screening, eg. subject #1, subject #2, subject #3 and so on. Based on the randomizer generated table, subject #1 will receive either placebo (#1 group) or study drug (#2 group). This will be repeated for each subject. For reproducibility purpose, we will document the final randomization schedule and the random SEED number used to generate the schedule. Randomization will be performed by the Illinois Eye and Ear Infirmary's pharmacy, and neither participants nor research staff will be aware of the assigned treatments. The person conducting the randomization will remain masked as well.

The study identification (ID) number will be used on all study-related documents. To maintain confidentiality, the subject's name will not be recorded on any study document other than the informed consent form. The drug vial number will be linked to the patient identification number.

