7.1 Sample Size Determination

Our intention is to have at least 30 subjects in each group (study drug/ vehicle) complete the study. This number is based on published reports of similar randomized clinical trials designed to determine

efficacy and tolerability of a test drug in Dry Eye Disease.³²⁻³⁴ A total of 72 subjects will be enrolled so that even if 20% of subjects are unable to complete the study, we will still remain with the intended number of subjects who complete the study (at least 30 subjects in each group). Subjects will be randomized to either of the two groups (#1, placebo; #2, study drug) as explained in section 5.3. However, all subjects who received at least two weeks of treatment with study eye drops and attended at least the first post-treatment (week 2) follow up visit will be included for analysis.

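### The chi-square test planned for the investigator's rating ignores the order of the seven-point CGI; an ordinal test would be more powerful against a consistent shift, at no data cost

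*Combined protocol and SAP*

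**What the plan says.** Section 7.2 (Statistical Methods): "Chi-square test will be used to compare qualitative variables". The same sentence gives the variables and the comparison in full: "Chi-square test will be used to compare qualitative variables (Investigator's rating scale/ changes in concomitant medications) between the 2 groups". The significance rule there is "Two-sided $P < .05$ will be considered statistically significant for all comparisons". The Wilcoxon test in 7.2 is a signed-rank test of OSDI against baseline, that is, a paired comparison. The chi-square is therefore the only hypothesis test that 7.2 names for comparing the two arms, although it also promises 95% confidence intervals for drug against placebo.

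Section 3.2.2 (CGI) has the physician rate change since baseline: "The responses will be categorized on a seven point scale as follows". The list then runs in order from marked worsening, through unchanged, to marked improvement.

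Section 3.2 (Primary Study Endpoints) places the CGI and the patient-rated SGA inside the primary efficacy endpoint, where they "will serve as anchors to OSDI".

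Section 7.1 (Sample Size Determination): "Our intention is to have at least 30 subjects in each group (study drug/ vehicle) complete the study". The number rests on precedent, and no power is stated for any endpoint.

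**The concern.** A Pearson chi-square statistic is unchanged if the seven column labels are shuffled. It asks whether the two distributions differ in any way and spends up to (2-1) x (7-1) = 6 degrees of freedom on that. The clinical question is directional: did subjects on drug improve more than subjects on vehicle? A test that uses the order puts that question into 1 degree of freedom.

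In a trial with about 30 completers per arm, the planned test could miss a moderate, consistent shift toward improvement that an ordinal test on the same data would more often detect. With seven categories and so few subjects, many expected counts also fall below 5, which raises the question of whether the chi-square approximation can be trusted.

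**Working it through.** **Which variable is meant.** Section 7.2 does not name the CGI. Section 3.2 describes the CGI as the physician's rating, section 3.2.2 has the principal investigator complete it, and no other investigator rating of change is described. Reading 7.2 as the CGI is an inference, but a fair one. No trend test, rank test, ordinal model or collapsing of categories is specified for it.

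**Inputs from the documents.** Seven categories (3.2.2); two-sided 0.05 (7.2); at least 30 completers per arm and 72 enrolled (7.1). The list in 5.3 is drawn "to generate 1 set of 72 non-unique, unsorted numbers with a range from 1 to 2", so arms are equal only in expectation; I use 30:30, and 36:36 as the no-dropout case. There is no stated power for the CGI to reproduce.

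**Inputs assumed.** The vehicle distribution and the effect. My reference vehicle distribution, from marked worsening to marked improvement, is 0.04, 0.08, 0.14, 0.34, 0.22, 0.12, 0.06. Five other shapes (spread, uniform, leaning to improvement, concentrated on unchanged, few worsening) give the ranges. The effect is a proportional-odds shift:

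logit P(Y <= k | drug) = logit P(Y <= k | vehicle) - log(OR).

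Example: the vehicle probability of unchanged or worse is 0.04 + 0.08 + 0.14 + 0.34 = 0.60, odds 1.5. At OR 3 the odds become 1.5/3 = 0.5 and the probability 0.5/1.5 = 0.33, so the proportion with any improvement rises from 40% to 67%.

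**Step 1: large-sample check.** Critical values are 3.84 (1 df) and 12.59 (6 df). At the same noncentrality, a 1-df test with 50% power (noncentrality 3.84) becomes a 6-df test with 26%; 60% becomes 33%, 70% becomes 41%, 80% (noncentrality 7.85) becomes 52%, and 90% becomes 67%. The proportion of power lost falls as the effect grows.

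**Step 2: simulation.** 20,000 trials per scenario; Pearson chi-square with df = non-empty categories minus 1, against the tie-corrected Wilcoxon rank-sum test, 30 per arm.

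| OR | Reference distribution: chi-square v rank-sum | Ratio | Range over five other shapes |
|---|---|---|---|
| 1.5 | 6% v 14% | 0.45 | 5.5-7.2% v 13-14% |
| 2 | 12% v 31% | 0.40 | 12-15% v 30-33% |
| 2.5 | 21% v 50% | 0.43 | 21-25% v 48-51% |
| 3 | 32% v 65% | 0.49 | 32-36% v 62-66% |
| 4 | 50% v 84% | 0.60 | 52-57% v 81-84% |
| 5 | 67% v 93% | 0.72 | 68-72% v 92-93% |
| 6 | 78% v 97% | 0.80 | 79-83% v 96-97% |

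At 36 per arm the reference distribution gives 15% v 37% (OR 2), 39% v 73% (OR 3) and 62% v 90% (OR 4).

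**Step 3: effects that are not a uniform shift.** If 20% of treated subjects move to marked improvement and the rest are unaffected, power is about 25% for both tests; if 30% move, it is about 50% for both. With a polarised response (more treated subjects at both ends) the order reverses: one such alternative gave 50% for chi-square against 7% for rank-sum.

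**Step 4: sparse cells.** Under no effect, the expected counts per arm for the reference distribution are 30 x p = 1.2, 2.4, 4.2, 10.2, 6.6, 3.6, 1.8, so five of seven are below 5. Across the scenarios at 30 per arm, 50-71% of category columns are below 5. The simulated size of the chi-square is about 2.6-4.3% against a nominal 5%.

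**Step 5: collapsed categories.** If the CGI were collapsed before testing, chi-square power at OR 3 would be 37-47% with three categories and 46-56% for improved against not improved, compared with 62-66% for the rank test on seven.

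**The case against.** The strongest objection is that the size of the loss is not a property of this plan. The documents state no CGI distribution, effect or power target. A reader might infer that the chi-square test simply halves power, and they do not support that. A loss of about half belongs to an assumed proportional-odds shift with an odds ratio up to about 3, which is the alternative that favours the rank test. At OR 4 the reference loss is 1 - 0.60 = 40%, and at OR 6 it is 20%. With a benefit confined to a subgroup reaching the top category there is no loss. All of this stands, and the figures must carry their conditions.

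Second, 7.2 does not say that all seven categories enter the table. That also stands. Collapsing would narrow the gap, but in the scenarios run it would not close it, and no grouping is pre-specified.

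Third, a reader might infer from the small expected counts that the test is invalid. It is not: its error rate is below nominal, so there is no excess of false positives, and the conservatism is already included in the simulated power.

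Fourth, a reader might infer that the SGA is affected in the same way. Section 7.2 assigns the SGA no chi-square test; it is a patient's rating, and no between-arm test is named for it.

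Finally, the Study Summary names OSDI change to week 8 as the primary efficacy measure. Using the CGI as an anchor to interpret the OSDI does not depend on a between-arm p-value. This limits the consequence. It does not make the chi-square test the better choice for the between-arm comparison that 7.2 itself plans.

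**Conclusion.** The point holds in a limited form. The planned test discards the order of a seven-point scale that is defined by its order, and nothing else in the plan restores it. If all seven categories are tested with 30 per arm and the effect is a consistent shift of odds ratio 2 to 3, power is about 12-36% against 30-66% for a rank-sum test; at odds ratio 4 it is about 50-57% against 81-84%. These figures rest on assumed distributions and a proportional-odds effect, neither of which the documents supply.

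This is an inefficient choice, not an invalid one. The consequence is modest, because no sample size or power rests on the CGI. Even the better test has only about 30-33% power at odds ratio 2, so changing the test would not make the trial well powered for a small CGI effect.

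**What to change.** In section 7.2, name the CGI and compare it between arms with a Wilcoxon rank-sum test or a proportional-odds model on all seven categories. The model also yields a common odds ratio with a 95% confidence interval. Keep the chi-square test, or Fisher's exact test where counts are small, for binary variables such as any change in concomitant medication. The same ordinal test can be used for the five-point SGA items. If collapsing the CGI is preferred, state the grouping before unblinding.

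The cost is one sentence, with no new data, visits or subjects. The downside is that an ordinal test has less power than chi-square against a polarised response, so the full distribution by arm should be tabulated alongside it.

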3.3 Secondary Endpoints

The secondary study endpoints will include:

1. Change in tear secretion as measured by Schirmer I test
2. The proportion of eyes achieving complete ocular surface staining clearance after treatment
3. Visual acuity change
4. Change in frequency of administration of artificial tears or concomitant eye drops
5. Change in number of corneal filaments (slit-lamp examination)

Corneal filaments are mucous tags that are adherent to the surface of cornea. The number of such mucus tags will be counted on each clinical examination (slit-lamp examination).

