5.6 Prior and Concomitant Therapy

Prior medications are defined as all medications taken within 30 days prior to Day 1, whether there is continued use or not. Concomitant medications must be identified in the patient's medical record, including all lubricants administered for Dry Eye Disease. These medications will be recorded in the case report form (CRF).

• For each medication taken, the following information will be collected:

1. Medication trade name
2. Eye that was treated, if applicable
3. Indication for which the medication was given

4. Date started
5. Date stopped
6. Dose of medication used.

There will be a 2-week washout period of topical corticosteroids and topical cyclosporine before enrollment and these medications are prohibited throughout the study. Other than these, participants will be permitted to continue their chronic DED treatments which include the use of artificial tears, eyelid massage, or warm compresses. The number of drops and frequency must be recorded in the patient diary provided.

- The use of any investigational agent during past 30 days is prohibited.

There is only one FDA approved treatment currently available to treat patients with Keratoconjunctivitis Sicca (dry eye disease)- Cyclosporine 0.05% (marketed as Restasis). The FDA approved indication for Restasis use is the following: “to increase tear production in patients whose tear production is presumed to be suppressed due to ocular inflammation associated with keratoconjunctivitis sicca”. Restasis will be withheld during the course of this study. This is necessary as the proposed mechanism of action of rhDNase in dry eyes is to reduce inflammation on the surface of the eye. Restasis can also reduce inflammation albeit via a different mechanism. Thus, because of over lapping anti-inflammatory actions, it may not be possible to attribute any observed clinical benefit to rhDNase treatment if Restasis is used concurrently. This approach has been used in other clinical trials that have investigated the use of an anti-inflammatory agent in dry eye disease.³²

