It is ethical to withhold Restasis because, as its FDA approved indication suggests, the clinical benefit of using Restasis is increased production of tears. While receiving DNase1, patients will continue to receive artificial tears as needed. Therefore, although the patients may not have an increase in tear production if Restasis is withheld, the ocular surface will receive sufficient lubrication and hydration due to the use of artificial tears.

Holding Restasis may increase the risk of worsening of DED during the wash-out period and during the course of the study. However, because artificial tears will be used during the wash out period as well as during the course of the study as needed, we do not expect any significant clinical worsening during the study. We do however expect the frequency of use of artificial tears to go up during the wash out period and during the course of the study.

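### Section 7.2 names no between-arm test that uses the size of the change in artificial-tear use (secondary endpoint 4); the one test that plausibly applies is a chi-square on undefined categories

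*Combined protocol and SAP*

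**What the plan says.** Section 3.3 lists as its fourth secondary endpoint: "Change in frequency of administration of artificial tears or concomitant eye drops".

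Section 5.6 lets subjects continue artificial tears, and on data capture it says: "The number of drops and frequency must be recorded in the patient diary provided". Concomitant medications are to be identified in the medical record, "including all lubricants administered for Dry Eye Disease".

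Section 7.2 names two tests:
- For numbers: "A Wilcoxon Signed-rank test will be used for paired comparison of quantitative variables (OSDI score) between the baseline and each post-baseline time points". This compares each time point with baseline, gives OSDI as its only example, and does not compare the arms.
- For categories: "Chi-square test will be used to compare qualitative variables". The examples given are the investigator's rating scale and "changes in concomitant medications) between the 2 groups". No categories are defined for the second.

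Three general sentences in 7.2 also reach this endpoint. Outcomes are framed as per-subject change: "We will define outcome measures on the basis of the change for each subject from baseline to each follow-up point", with control for chance baseline imbalance. Descriptive statistics are promised for secondary endpoints. So is a 95% CI comparing drug with placebo, with no effect measure or method stated.

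The synopsis mentions a Wilcoxon test only for subjective symptoms.

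**The concern.** The endpoint is a quantity and its data are collected as numbers, but the named comparison between arms treats the variable as a category. A subject who goes up by one drop a day and a subject who goes up by four fall in the same cell. If the cells are changed and unchanged, a subject who cut down is also counted with one who needed more.

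The endpoint carries information worth keeping. Sections 5.6 and 5.7 list more frequent artificial tears first among the options when dry eye worsens, so a difference between arms in tear use would be a fairly direct sign of benefit. Section 5.6 also forecasts a rise: "We do however expect the frequency of use of artificial tears to go up during the wash out period" and during the study. If use rises in both arms, the arms may differ mainly in how much it rises, which is what a chi-square cannot see.

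**Working it through.** The plan gives no effect size, SD or power for this endpoint, so it has no figure of its own to reproduce. The effect sizes, SDs and distributions below are assumptions.

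**1. Does the chi-square belong to endpoint 4?** Section 7.2 does not name artificial tears. Section 5.6 places lubricants for dry eye among concomitant medications, and no other endpoint in 3.3 concerns concomitant treatment. The link is therefore a well-supported inference. If it is wrong, endpoint 4 has no named between-group test at all.

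**2. Is size lost?** Suppose 18 of 30 subjects in each arm increase and 12 do not change. The table is [12, 18; 12, 18], so the chi-square is 0 and p = 1.0, whether the increases are 1 drop in one arm and 4 in the other or the same in both.

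**3. Is direction lost?** It is under changed/unchanged and is not under decreased/unchanged/increased. The plan does not say which coding applies.

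**4. Power if change is spread continuously.**
- Inputs: 36 per arm (72/2, from 3.1 and 7.1, assuming equal arms); two-sided 0.05 (7.2). Assumed: change in drops/day is normal with SD 2, rounded to whole drops.
- Share changed at mean m: 1 − [Φ((0.5 − m)/2) − Φ((−0.5 − m)/2)].
  - m = 0: 1 − [Φ(0.25) − Φ(−0.25)] = 1 − 0.197 = 80%
  - m = 1.5: 1 − [Φ(−0.5) − Φ(−1)] = 1 − 0.150 = 85%
  - m = 3: 1 − [Φ(−1.25) − Φ(−1.75)] = 1 − 0.066 = 93%
- Simulated power (3,000 to 4,000 trials per setting, uncorrected chi-square, Monte Carlo error of 1 to 2 points):

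| Vehicle vs drug mean change | Yes/no chi-square | Three-category chi-square | Rank-sum |
|---|---|---|---|
| +1.5 vs 0 | 8% | 65% | 86% |
| +3 vs +1.5 (both arms rise) | 23% | 46% | 86% |
| +1 vs 0 | 6% | 33% | 52% |

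A separate run at 30 per arm, with a difference of 0.8 SD and SDs of 1.5 to 3, gave 5–18%, 56–67% and 83–84%.

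**5. Power if many subjects keep their usual routine.** Assumed: increases of 1 to 4 drops, decreases of 1 to 2, 36 per arm.

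| Unchanged/up/down: vehicle vs drug | Yes/no chi-square | Three-category chi-square | Rank-sum |
|---|---|---|---|
| 40/50/10 vs 70/15/15 | 73% | 85% | 80% |
| 40/55/5 vs 75/20/5 | 87% | 83% | 78% |

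**6. Comparison of losses.** In the first two rows of step 4, the chi-square gives up 86 − 8 = 78 points at worst under yes/no coding and 86 − 46 = 40 points under three categories. In step 5, the rank-sum gives up at most 87 − 78 = 9 points to the better chi-square.

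**The case against.** The strongest reply has four parts.

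- **The chi-square is not the plan's whole analysis.** A reader might infer that it is. The text does not support that: 7.2 also promises descriptive statistics and a drug-versus-placebo 95% CI on change from baseline for secondary endpoints, and these could preserve both size and direction. This stands. It does not close the gap, because with no effect measure stated the CI could equally be for a difference in proportions.
- **The chi-square may be meant for something else.** The visit sections use similar words for a general record of medication changes, where starts and stops are naturally categorical. This is possible. Endpoint 4 would then lack a named test and would need the same addition to 7.2.
- **Saturation is not shown.** A reader might infer from the forecast in 5.6 that nearly everyone in both arms will count as changed. The forecast is made in the context of withholding Restasis, and the documents do not say how many subjects that affects. Section 6.5.1 allows for subjects who need no washout, and a rise during washout comes before Day 1. The changed/unchanged coding is itself assumed. This stands.
- **The power loss is not general.** Step 5 shows the ordering can reverse when many subjects do not change. This stands too, so no single power figure should be quoted as the cost of the plan.

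It is also one of five secondary endpoints in a Phase I/II trial, and no primary conclusion rests on it.

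**Conclusion.** The point holds in a limited form. Endpoint 4 is defined by an amount of change, the data for it are collected, and the only named between-arm test that plausibly applies discards that amount under any coding by direction or by any change. Whether direction is lost as well depends on a coding the plan does not give.

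The size of the loss is conditional. For a 1.5-drop difference with SD 2 and 36 per arm, power is about 8–23% (yes/no) or 46–65% (three categories), against 86% for a rank-sum test. With many unchanged subjects there may be no loss, or a small gain for the chi-square. The documents do not support saying that the trial will miss a real difference, or that the chi-square is the only analysis planned. They do support saying that the stated test does not match the stated endpoint. In the settings tried, the risk is lopsided: up to 78 points lost with the chi-square, against up to 9 with the rank-sum. This should be corrected, but it does not threaten the primary analysis.

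**What to change.** In 7.2, state for secondary endpoint 4:

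- **Variable:** the per-subject change in mean daily instillations of artificial tears and other concomitant eye drops, over a set diary window, for example the 7 days before Week 8.
- **Comparison:** drug versus vehicle by Wilcoxon rank-sum test with a Hodges-Lehmann 95% CI, or by ANCOVA on baseline frequency with a CI for the adjusted mean difference. Choose one in advance. This also gives the CI already promised in 7.2 its effect measure.
- **Baseline source:** the diary is issued after the first dose (6.5.2), and the medication items listed in 5.6 include dose but not frequency. State where and when the pre-dose frequency is recorded, for example on the CRF at the Day 1 visit before dosing.
- **Chi-square:** keep it for categorical items, such as starting or stopping a named medication, and define the categories.

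The cost is a few lines of text and one baseline entry. No new visit or procedure is needed, since the diary already asks for number and frequency. The small downside is that diary counts must be entered as numbers.
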